1.0 Objectives/ Specific Aims

Our study aims to compare the efficacy of a deep-layer, knotless closing method using the Dermabond PRINEO skin closure device (2-octyl cyanoacrylate adhesive glue in combination with self-adhesive polyester mesh tape) to the current practices of wound closure after total joint arthroplasty. While surgeons utilize a variety of incision closure techniques, most use a layered closure with deep fascial closure consisting of interrupted, knotted sutures combined with either staples (Figure 1) or sutures (Figure 2) for superficial closing. In this Phase 4 clinical trial, we hypothesize that the Dermabond PRINEO wound closure system with running knotless sutures for deep and superficial closure (Figure 3) will significantly reduce closure time in the operating room and achieve similar or better incision healing after shoulder arthroplasty.

Primary aims:

1.1 Aim 1: To quantify differences the time required for wound closure with the PRINEO closure method (Figure 3) and that of traditional closure methods (interrupted deep fascial suture with either subcuticular sutures and traditional Dermabond (Figure 2) or metal staples for superficial closure (Figure 1)

H_0 : There are no differences in wound closure times between PRINEO and subcuticular sutures or metal staples in time to close incisions

H_A : There are differences between PRINEO and subcuticular sutures or metal staples in time to close incisions such that staples will be significantly faster than PRINEO and PRINEO will be significantly faster than sutures.

1.2 Aim 2: To quantify differences between PRINEO and subcuticular sutures or metal staples in wound healing over three postoperative follow-up points

H_0 : There are no differences between PRINEO and subcuticular sutures or metal staples in wound healing (dehiscence and drainage) over three postop follow-up points.

H_A : There are differences between PRINEO and subcuticular sutures or metal staples in wound healing (dehiscence and drainage) over three postop follow-up points such that PRINEO demonstrates superior healing to both sutures and staples.

Exploratory Aims:

1.3 Aim 3: To quantify differences between PRINEO and subcuticular sutures or metal staples in observer-evaluated and patient-evaluated cosmetic outcomes for the surgical scar over four postoperative follow-up points

H_0 : There are no differences between PRINEO and subcuticular sutures or metal staples in cosmetic outcomes over four postop follow-up points.

H_A : There are differences between PRINEO and subcuticular sutures or metal staples in wound healing (dehiscence and drainage) over four postop follow-up points such that PRINEO demonstrates superior cosmetic outcomes to both sutures and staples.

1.4 Aim 4: To quantify differences between PRINEO and subcuticular sutures or metal staples in complication rates (defined as allergic reaction, inflammation, irritation, drainage, or infection)

H_0 : There are no differences between PRINEO and subcuticular sutures or metal staples in wound complication rates over four postop follow-up points.

H_A : There are differences between PRINEO and subcuticular sutures or metal staples in wound complication rates.

1.5 Aim 5: To evaluate the overall cost-effectiveness of PRINEO for wound closure relative to subcuticular sutures and metal staples

H_0 : There are no differences between PRINEO, subcuticular sutures, and metal staples in cost-effectiveness over four postop follow-up points.

[figure not shown]
H_A : There are differences between PRINEO, subcuticular sutures, and metal staples in cost-effectiveness such that staples are superior to PRINEO and PRINEO is superior to subcuticular sutures.

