3.0 Intervention to be studied

Specifically, in the 510(k) cleared Dermabond PRINEO skin closure system (Ethicon Inc.), the 2-octyl cyanoacrylate adhesive is used in combination with a polyester mesh tape, either 22cm or 60cm in width. This mesh tape is designed to provide for tighter sealing of the incision and may further protect against discharge in more mobile wounds. Use of the tape may strengthen the wound closure and also simplify and improve alignment and apposition of wound edges [[12] and Ethicon internal testing]. Several prospective randomized, controlled trials have demonstrated consistently lower wound closing times and equivalent or significantly improved cosmetic outcomes and complication rates with this system [13-16]. More flexibility in application due to “body-contouring” has also been noted [17].

Observational studies of the PRINEO system report success use of the device as evaluated by surgeon and patient satisfaction [11, 17, 18]. Research of the PRINEO system used after total joint replacement are at present limited to retrospective studies [11, 18] and case reports of allergic reactions [19, 20].

[name] currently closes incisions after shoulder arthroplasty with metal staples, and [name] currently closes incisions after shoulder arthroplasty using subcuticular sutures with Dermabond. Both surgeons use interrupted deep-layer sutures. This study will consist of two parallel comparisons to these distinct control arms. The PRINEO closing method, which utilizes running deep and superficial sutures with Dermabond PRINEO, will be directly compared to each surgeon’s wound closure technique, as half of each surgeon’s patients will be randomized to the PRINEO treatment condition while the other half continue to undergo wound closure with the current technique utilized by the

surgeon. This will result in two parallel treatment arms and two distinct control arms (Fig. 1). Both surgeons have significant experience in the application of Dermabond PRINEO for wound closure.

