4.0 Study Endpoints

The duration of wound closure is primary endpoint for this study. Wound closure timing outcomes will be collected in the operating room towards the conclusion of each surgery. Closure time is the time between the first stitch for closure and the completion of application of dressing to the wound. The incision length will be measured to calculate time per centimeter.

Cost per minute of operation time is another endpoint for the study. It will be conservatively approximated using existing reports of personnel capacity rates for orthopaedic surgeon. Cost-effectiveness analysis will be conducted by comparing the total cost of all wound closure materials for each technique, and a cost per minute applied to wound closure time.

Wound outcomes, both clinical and cosmetic, will be another primary endpoint for this study. Patient-centered outcomes for wound and scar evaluation will be collected at 6 weeks and 3 month postoperative appointments in clinic. These outcomes will be measured using the Modified Hollander Cosmesis Scale [14, 21], the Patient and Observer Scar Assessment Scale (POSAS) [14, 22, 23], and the Acute Inflammatory Response Evaluation (AIRE) score as described in the 2015 study by Blondeel et al [14].

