10.0 Study Design/ Methods

Randomization will take place the morning of surgery based on a randomly organized, computer-generated order.

Patients in [name] clinic will be randomized to one of two treatment conditions for wound closure after shoulder arthroplasty: 1) deep layer closure with 0-0 vicryl interrupted sutures followed by superficial skin closure with metal staples with aquacel dressing and 2) deep layer closure with a running 2-0 unidirectional Stratafix suture followed by superficial closure with subcuticular bidirectional 3-0 Stratafix suture followed by the Dermabond PRINEO (60cm or 22cm polyester mesh and 2-octyl cyanoacrylate adhesive) with Medipore and folded 4x4 cotton gauze dressing.

Patients in [name] clinic will be randomized to one of two treatment conditions for wound closure after shoulder arthroplasty: 1) deep closure with interrupted 2-0 vicryl sutures followed by a running subcuticular bidirectional 3-0 Stratafix with Dermabond and Medipore dressing with folded 4x4 cotton gauze dressing and 2) deep layer closure with a running 2-0 unidirectional Stratafix suture followed by superficial closure with subcuticular bidirectional 3-0 Stratafix suture followed by the Dermabond PRINEO (60cm or 22cm polyester mesh and 2-octyl cyanoacrylate adhesive) with Medipore and folded 4x4 cotton gauze dressing.

The rationale for investigating the current practice of deep closure with interrupted sutures is as follows: Using running suture introduces a potential risk of wound dehiscence if the suture fails at any juncture despite the presence of the barbs. The Dermabond PRINEO represents a powerful closure mechanism that in all probability eliminates the risk of wound dehiscence regardless of the skin closure method. Therefore, using a rapid wound closure method with deep layer running sutures is now a possibility with the Dermabond PRINEO that was not available before.

Patients will not be made aware of the treatment they are randomized to until their first follow up visit or when wound dressing is removed to reveal the device used for wound closure.

At the conclusion of the surgery, the assigned wound closure technique will be implemented. The following data points to measure the primary outcome, wound closure efficiency, will be collected in the operating room:

1. Total operating time in minutes and seconds, from the first incision to the application of wound dressing.

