2. Total time for wound closure in minutes and seconds, from the first stitch for closure to the application of wound dressing.
3. The incision length in centimeters

4. The cost of materials utilized for wound closure (suture, Dermabond, PRINEO, staples, dressings, etc.)

All patients will be seen in clinic 2 weeks post operatively during which time the wound closure technique (sutures, or staples) will be removed by a nurse according to the manufacturer and standard technique. The patients who are randomized to Dermabond PRINEO will be instructed to keep their polymer mesh on for an additional 2 weeks after their 2 weeks visit. Any complications such as drainage, acute inflammation, or signs of infection will be recorded at this time and treated per clinical standards. The following data points to measure wound clinical and cosmetic outcomes, will be collected at 6 weeks and 3 months postoperatively:

1. mHCS score
2. AIRE score
3. POSAS score
4. Complications and adverse events

mHCS, AIRE, and POSAS scores are all dependent on aspects of the physical exam, such as evaluation of pliability, temperature, edema, pain, and contour. To mitigate any observer bias, all incisions will be photographed and additionally evaluated by a plastic surgeon ([name]) blinded to the treatment condition using the POSAS-Observer characteristics which may be assessed through standardized photography alone (Vascularity, Pigmentation, Thickness, Relief, Surface Area, and Overall Opinion).

A medical record review will also be performed to collect the following data: Age; gender; BMI (including height and weight), race, diabetes status (type, insulin dependency, years diagnosed); history of smoking/tobacco use; frequency of alcohol consumption.

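### Section 1.0 hypothesises similar or better healing, but Aim 2 tests superiority with no margin or interval rule, and dehiscence is assigned to no test

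*Combined protocol and SAP*

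**What the plan says.** - **Overall hypothesis (Section 1.0).** PRINEO is expected to shorten closure and to "achieve similar or better incision healing after shoulder arthroplasty".
- **Aim 2 (Section 1.2, a primary aim).** Healing is defined as dehiscence and drainage over three follow-up points. The null is no difference; the alternative is that "PRINEO demonstrates superior healing to both sutures and staples".
- **Aim 4 (Section 1.4, exploratory).** It concerns "complication rates (defined as allergic reaction, inflammation, irritation, drainage, or infection". Drainage is on that list and dehiscence is not.
- **Design (Section 3.0).** "This study will consist of two parallel comparisons to these distinct control arms", with half of each surgeon's patients randomised to PRINEO.
- **Endpoints (Section 4.0).** "Wound outcomes, both clinical and cosmetic, will be another primary endpoint for this study". The same paragraph measures these outcomes with mHCS, POSAS and AIRE at 6 weeks and 3 months.
- **Rationale and data collection (Section 10.0).** "Using running suture introduces a potential risk of wound dehiscence if the suture fails at any juncture", while PRINEO "in all probability eliminates the risk of wound dehiscence regardless of the skin closure method". At the 2-week visit, "Any complications such as drainage, acute inflammation, or signs of infection will be recorded at this time". Complications and adverse events are collected again at 6 weeks and 3 months.
- **Analysis (Section 11.0).** Two-sample t-tests for closure time, ANOVA with Tukey HSD for mHCS, AIRE and POSAS, and chi-square for complication rates. The sample-size justification covers closure time only. The data-sheet sentence gives 6 weeks and 3 months as the visits.

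**The concern.** The conclusion that Section 1.0 hopes for and the one that the methods can deliver are different. *Similar or better* needs a statement of how much worse would still count as similar, and an interval to compare with it. The plan has neither. If the wound tests are non-significant, the trial has not shown similarity; it has only failed to show a difference.

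The gap matters most for dehiscence. Section 10.0 names it as the risk that comes with the running deep suture and asserts that PRINEO very probably removes it. Aim 2 is where that assertion would be checked, yet no sentence defines, records by name or tests dehiscence. At stake is whether the trial can say anything pre-specified about the main wound risk that the protocol itself raises.

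**Working it through.** **1. The plan's own figure.** Section 11.0 gives an effect size of 0.93, alpha 0.05 and power 0.80. The two-sided normal formula is n per group = 2(1.960 + 0.842)² / 0.93² = 15.70 / 0.865 = 18.2, rounded up to 19, and 4 × 19 = 76. The stated 19 and 76 reproduce, but they concern closure time. The only relevance thresholds in the documents (5, 7.5 and 10 minutes) also concern closure time. Nothing equivalent exists for healing.

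**2. Outcome by outcome.**

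| Outcome | Where it is an aim or endpoint | Named data item? | Named test |
|---|---|---|---|
| Dehiscence | Aim 2 (primary) | No; the open-ended 2-week wording or adverse events could capture it | None assigned |
| Drainage | Aim 2 (primary); part of Aim 4 | Yes, at 2 weeks; later only under complications | Chi-square, only inside the Aim 4 composite |
| mHCS, POSAS, AIRE | Section 4.0 primary wound endpoint | Yes, 6 weeks and 3 months | ANOVA with Tukey HSD |
| Complications | Aim 4 (exploratory) | Yes | Chi-square |

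The scales have a test, but no sentence links them to dehiscence or drainage.

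**3. What a non-significant test would mean.** The documents give no dehiscence, drainage or complication rate, so every rate below is assumed. Method: exact binomial enumeration, Pearson chi-square without continuity correction, two-sided 0.05, full arms. 22 v 22 is the within-surgeon comparison. 44 v 44 is simple pooling, as an approximation to a surgeon-stratified analysis.

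| Control v PRINEO | Non-significant, 22 v 22 | Non-significant, 44 v 44 |
|---|---|---|
| 5% v 15% | 82% | 62% |
| 5% v 20% | 67% | 38% |
| 5% v 40% | 14% | 1% |

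A very large excess would usually be detected; a tripling from 5% often would not.

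**4. No events in either arm.** The Wilson upper limit for 0/n is z²/(n + z²), with z² = 3.84. For n = 22 it is 3.84/25.84 = 14.9%; for n = 44 it is 3.84/47.84 = 8.0%. With zero events in both arms, the Newcombe 95% interval for the difference is therefore ±14.9 points (22 v 22) or ±8.0 points (44 v 44).

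**5. What an interval rule could achieve.** Chance that the upper Newcombe 95% limit falls below a given excess when both true rates are equal, at 44 v 44:

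| True rate in both arms | 10-point excess ruled out | 15-point excess ruled out |
|---|---|---|
| 1% | 75% | 95% |
| 2% | 64% | 89% |
| 5% | 44% | 75% |

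The margin that can be met depends on the event rate. At 22 v 22 with both rates at 5%, the corresponding chances are 11% and 44%.

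**6. Why the rule must say that the interval governs.** With 4/22 v 0/22, chi-square gives p = 0.036, while the Newcombe interval runs from −0.2 to +38.5 points and includes zero. Without a stated priority the two could be reported differently.

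**The case against.** The strongest reply is that *similar or better* is introductory narrative. The formal hypotheses follow it, the named tests match them, and no sentence says that a non-significant result will be read as similarity. That is correct, and a reader who infers that the sponsor intends such a reading goes beyond the text. But Section 1.0 words it as the trial's hypothesis, and nothing in the plan says what would confirm its *similar* half.

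A reader might also infer that dehiscence will go unanalysed. The documents do not go that far. The 2-week wording is open-ended, adverse events are collected later, and the analysis paragraph tests complication rates without repeating Aim 4's list. Dehiscence could reach the chi-square test by that route. What stands is that no sentence sends it there and Aim 4's definition leaves it out.

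Nor is it right that the primary wound endpoint has no analysis: Section 4.0 measures it by three scales that are tested. Nor does Aim 2 lack a third visit: Section 10.0 records complications at 2 weeks, 6 weeks and 3 months, and only the data-sheet sentence in Section 11.0 omits the first.

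Finally, it can be said that the figures rest on assumed rates and that the protocol expects dehiscence with PRINEO to be very rare. This has force. It means the trial cannot be said to support only a wide margin; at true rates of 1% to 2% the pooled interval would rule out a 10-point excess in most trials. It does not supply the missing rule.

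**Conclusion.** The concern holds in this form: the named methods cannot support the *similar* half of the Section 1.0 hypothesis, and dehiscence, one of two components of a primary aim, is assigned to no test. Both follow from the text and need no assumption. The size does rest on assumptions (illustrative rates, full arms, simple pooling): at 5% v 15%, non-significance in 82% of trials within surgeon and 62% pooled; with no events at all, about ±15 and ±8 points still open. Losses to follow-up would widen these intervals. The plan should be changed on this point, but the powered closure-time comparison is not affected.

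**What to change.** 1. Align Section 1.0 and Aim 2, so that both state the same healing claim.
2. Name and define dehiscence and drainage as recorded items at the existing 2-week, 6-week and 3-month visits, and add 2 weeks to the data-sheet sentence in Section 11.0.
3. For each of the two, report the risk difference within each surgeon and a surgeon-stratified pooled risk difference, labelled PRINEO v surgeon's usual closure, with 95% confidence intervals by one score or Newcombe method named in advance. Report score differences with 95% confidence intervals.
4. State that the interval governs and that a non-significant test will not be reported as *similar*. Use *not worse* or *similar* for an outcome only if its interval lies within bounds that the sponsor names in advance for that outcome: the upper limit for *not worse*, both limits for *similar*. An interval wholly on one side of zero is reported as better or worse. Anything else is *inconclusive*, with the excess not excluded.
5. State how patients lost before 3 months are counted.

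**Cost.** No extra patients or visits. Two named data items, six binary intervals (two outcomes × three comparisons) and about 18 score intervals (three scales × two visits × three comparisons; more if the POSAS parts are separate). All should be labelled as unadjusted for multiplicity. For rare events the chance of wrongly excluding zero is well below nominal: with both rates at 5%, 0.3% per interval at 22 v 22 and 1.7% at 44 v 44. The score intervals carry the usual 5% each, so about 18 × 0.05 = 0.9 would exclude zero by chance if there were no true differences. The healing claim may also turn out weaker than Section 1.0 now suggests.

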2.0 Background

Figure 1. [name] treatment arm – control closure system.

Deep layer – interrupted sutures

- Interrupted sutures (0-0 vicryl)
- Placed completely under the epidermal skin layer
- Not removed post-operatively

[figure not shown]

Aneskey.com, adapted from Singer AJ, Hollander JE: *Lacerations and acute wounds*. Philadelphia, 2002, FA Davis.

Adapted from Yasuda et al (2017)

Superficial layer – metal staples

- Removed Post-Operatively 10-14 days

[figure not shown]

Pablo Paul / Alamy Stock Photo

Figure 2. [name] treatment arm – control closure system.

Deep layer – interrupted sutures

[figure not shown]
- Interrupted sutures (2-0 vicryl)
- Placed completely under the epidermal skin layer
- Not removed post-operatively

Subcuticular suture. Wikimedia Commons.
Dermabond, Sutureonline.com

Superficial layer - subcuticular sutures

- Running, subcuticular sutures (32-0 Stratafix)
- Traditional Dermabond applied to incision

[figure not shown]

Aneskey.com, adapted from Singer AJ, Hollander JE: *Lacerations and acute wounds*. Philadelphia, 2002, FA Davis.
Adapted from Yasuda et al (2017)

Figure 3. Dermabond PRINEO closure system.

Deep layer – running sutures

[figure not shown]
- Running, unidirectional sutures (2-0 Stratafix)
- Placed completely under the epidermal skin layer
- Not removed post-operatively

Adapted from Stratafix Best Practices Video, Youtube
Adapted from Yasuda et al (2017)

Superficial layer – subcuticular sutures + Dermabond PRINEO

- Running, bidirectional sutures (3-0 Stratafix)
- Dermabond PRINEO (60cm) or (22cm)

Subcuticular suture. Wikimedia Commons
Dermabond PRINEO, ethicon.com

A wound closure system requires proper closure of both deep and superficial tissue.

Traditionally, knotted (interrupted) sutures are used for deep layer closures, in combination with either staples or subcuticular sutures for superficial skin closure. However, tissue adhesives such as Dermabond PRINEO act as an effective microbial barrier and effectively prevents wound dehiscence. With Dermabond PRINEO, running sutures can be used for both deep and

superficial closing, saving significant time. In this proposal, we define the PRINEO skin closure system as one that uses running unidirectional sutures for deep layer sutures and running bidirectional suture for superficial skin closure, followed by the Dermabond PRINEO with Medipore and 4x4 cotton gauze as additional wound dressing.

Tissue adhesives like PRINEO are well-researched as alternatives for wound closure [1-5]. The common tissue adhesive, 2-octyl cyanoacrylate (OCA), has been used in surgical procedures since the 1950s and was FDA approved for use in wound closure in 1998 [6]. The OCA adhesive has been shown to reduce operating time, produce similar or improved cosmetic outcomes, similar or improved dehiscence and infection rates, and concurrent reduction in costs relative to the standard subcuticular suture method of closure [7-10]. The adhesive is also more flexible, allowing for easier application to incisions which span the joint [11].

Although the PRINEO system is not uncommonly used for wound closure after joint replacement, there is limited research to document the relative outcomes of a PRINEO closing system in contrast to other methods. This prospective study will randomize shoulder arthroplasty patients to wound closure with the PRINEO adhesive-mesh system, metal staples, or by subcuticular system to determine the relative efficacy, safety, and cosmetic outcomes of the Dermabond PRINEO system for the shoulder. As the delto-pectoral incision for shoulder arthroplasty can be a visible scar and the shoulder joint is highly mobile, the successful implementation of the PRINEO system may have substantial effects on patient satisfaction with their wound healing and surgical scar.

The efficiency and outcome of wound closure has also significance to operating room and clinic staff alike. Improving efficiency of wound closure, which may be particularly time consuming for long incisions in major surgery such as joint replacement, has cumulative effects in improving operating room flow and schedule adherence, and potentially, allowing for additional caseload. Removing sutures post-operatively may also be a time consuming process for clinic staff, in addition to being a source of discomfort for patients [1]. For this reason, interventions to optimize wound closure and ease of care are a highly relevant area of research.

[figure not shown]

Figure 4: Outline of study design

